6.2. Secondary Endpoints

The secondary endpoints of this study will compare the following assessments on the emPOWER Ankle to the subject’s passive prosthesis at Baseline (before wearing the emPOWER, when available) and Crossover:

- 12 minute Walk Test (12MWT)
- 10 meter Walk Test (10MWT)
- L-Test for overall mobility and fall risk
- Time and Quality of Ramp Ascent
- Time and Quality of Ramp Descent
- Activities-specific Balance Confidence (ABC) Scale
- Falls Efficacy Scale
- Amputee Mobility Predictor (AMP) Assessment
- Prosthetic Limb Users Survey of Mobility (PLUS-M) (12 item Short Form)
- Patient-specific Functional Scale (PSFS)
- Numeric Pain Rating Scale (NPRS)
- Activity monitoring
- Falls
- Activity Diary
- PROMIS Physical Function (Custom)
- PROMIS Global Health Short Form
- PROMIS Fatigue Short Form (7a)
- PROMIS Pain Intensity Short Form (3a)

Long term follow-up of subjects who agree to continue wearing the emPOWER Ankle at 3, 6 and 12 months with all outcome measures (except the diaries of activity and falls at 6 & 12 months).

7. Study Population

7.1. Selection Criteria

Study inclusion and exclusion criteria for the study are included in Table 7.1.1 below. Prior to enrollment in the study, a subject must meet all of the inclusion criteria and none of the exclusion criteria.

Table 7.1.1: Selection Criteria

| |
|--------------------|
| Selection Criteria |
|--------------------|

| Selection Criteria | |
|---------------------------|---|
| Inclusion Criteria | 
 I-1. Male and Female I-2. 55 years or older I-3. Subjects with transtibial amputations of either leg at least 1-year prior I-4. Suction or elevated vacuum suspension and Socket Comfort Score of at least 6 I-5. Sock fluctuation of ≤ 8 ply per day I-6. K-level rating of 3 or 4 based on the AMP score I-7. Ability to walk at a walking speed of > 0.75 meters per second with the current prosthesis I-8. Unilateral amputees (up to 7 bilateral amputees can be included, 1 per site in addition to the unilateral amputees) I-9. Foot size: 25-30 cm I-10. Ability to complete a continuous 6MWT I-11. Ability to provide written, informed consent I-12. Ability to complete study visits and study documents I-13. Ability to manage the complexity of a powered device including charging and changing batteries as needed I-14. Ability to read and understand English |
| Exclusion Criteria | 
 E-1. Subjects who have never used a prosthetic device E-2. Less than 55 years of age E-3. Weight <150 lbs. or > 287 lbs E-4. Transfemoral amputees E-5. Active sores or ulceration on subject's residual limb E-6. Sore on contralateral foot E-7. Cuff-link socket suspension E-8. Socket Comfort Score of less than 6 E-9. Sock fluctuation of > 8 per day E-10. K level of 1 or 2 E-11. Amputation clearance < 8.625" E-12. History of stroke or TIA that impairs current walking E-13. Recent history of excessive falling defined as more than 2 falls requiring medical assistance in the prior year |

| Selection Criteria | |
|--------------------|---|
| | E-14. Medications potentially affecting balance |
| | E-15. Recent hospitalization (within past 3 months) |
| | E-16. Cognitive deficiency that would impact ability to charge and change batteries as needed |

7.2. Subject Discontinuation or Withdrawal

- Subjects may voluntarily withdraw from the study at any time without reason. All information relative to the withdrawal must be fully documented in the subject’s chart.
- Subjects withdrawn prior to the study phase where they walk on the emPOWER Ankle will be replaced.

7.3. Subject Enrollment

The study will enroll up to ten (10) subjects into Phase I. Subjects will then be invited to participate in Phase II, long-term follow-up. The Study Site will be asked to enroll subjects with a unilateral transtibial amputation (on either the left or right side).

8. Concomitant Medication

All current medications will be recorded at study enrollment and any changes during the study period will be noted.

9. Study Visits

This is a pilot, prospective, cross-over, open label observational study that aims to enroll five (5) subjects at one (1) study site. The study will have two (2) study phases:

Phase I will include all subjects enrolled in the study and followed through emPOWER Follow-up (Visit 3).

Subjects who show benefit from the emPOWER Ankle will be offered the opportunity to continue to use the emPOWER Ankle after the study and participate in Phase II – Long-term follow-up through 12 months.

The schedule of assessments is shown below in Table 9.11.1, and study assessments are detailed in Section 10.

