2. Ensure that the study is not commenced until all necessary approvals have been obtained.
3. Ensure that a written informed consent is obtained from each subject prior to any data collection using the most recent IRB/EC approved subject Informed Consent Form (ICF).
4. Provide all required data and reports, as well as agree to allow source document verification of study data with subject’s medical records by a BionX, designee and/or any regulatory authorities.
5. Allow BionX personnel or its designees, as well as regulatory representatives, to inspect and copy any documents pertaining to this clinical investigation according to the federal, state, and institutional data and privacy protection laws.

Investigator Signature

I have read and understand the contents of the study and agree to abide by the requirements set forth in this document.

Investigator Name (print)

Study Center (print)

Investigator Signature

Date

Protocol Synopsis

EmPOWERing Active Seniors with Energy

| | |
|---------------------------------------|--|
| Study Population | The study population will include up to ten (10) unilateral transtibial amputees. |
| Intended Use | The device is intended to replace a missing foot and ankle. The emPOWER Ankle is to be used exclusively for fittings of lower-extremity amputations as prescribed by a healthcare professional. |
| Control | Subjects serve as their own control with assessments using their prescribed passive lower-extremity prosthesis at Baseline and after 2 weeks of re-accommodation after 3 months of use of emPOWER. |
| Study Design | This is a pilot, prospective, cross-over, open label observational study. Phase I: Screening through 3 Months Phase II: Long-term follow-up of subjects using the emPOWER Ankle in their daily lives from 3 Months through 12 Months |
| Primary Objective | The primary objective of this study is to characterize the increase in the distance subjects can walk during a six (6) minute period while wearing the emPOWER Ankle compared to a passive lower-extremity prosthesis. |
| Primary Effectiveness Endpoint | The primary endpoint of this study will be an improvement in walking distance with the emPOWER Ankle compared to the distance walked with the subject’s passive prosthesis as shown by 6 minute Walk Test (6MWT) results at 3 months. |

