| Secondary Endpoints | The secondary endpoints of this study will compare the following assessments on the emPOWER Ankle to the subject’s passive prosthesis at Baseline (before wearing the emPOWER, when available) and Crossover: 
 • 12 minute Walk Test (12MWT) • 10 meter Walk Test (10MWT) • L-Test for overall mobility and fall risk • Time and Quality of Ramp Ascent • Time and Quality of Ramp Descent • Activities-specific Balance Confidence (ABC) Scale • Falls Efficacy Scale • Amputee Mobility Predictor (AMP) Assessment • Prosthetic Limb Users Survey of Mobility (PLUS-M) (12 item Short Form) • Patient-specific Functional Scale (PSFS) • Numeric Pain Rating Scale (NPRS) • Activity monitoring over two weeks prior to the assessment session |

| | |
|--|--|
| | 
with the emPOWER Ankle and the re-assessment session with the previous foot using a Fitbit monitor.
 
 • Falls: Diary of reported falls for two weeks • Activity Diary to allow for self-reporting of activities of daily living and unique user experiences with the emPOWER Ankle for two weeks • PROMIS Physical Function (Custom) • PROMIS Global Health Short Form • PROMIS Fatigue Short Form (7a) • PROMIS Pain Intensity Short Form (3a) 
Long-term follow-up of subjects who agree to continue wearing the emPOWER Ankle at 3, 6 and 12 months with all outcome measures (except the activity monitoring and diaries of steps, activity and falls at 6 & 12 months).
 |
| 
Number of Subjects and Number of Study Sites
 | 
Up to ten (10) subjects will be enrolled into this study at one (1) study site.
 |
| 
Study Duration
 | 
Overall study enrollment is estimated to take two (2) months. The subject's study participation duration will last approximately four (4) months for the first phase. If the subject elects to continue in the second phase, that will last for an additional 9 months.
 |

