| 
Key Inclusion Criteria
 | 
 I-1. Males and females I-2. 55 years or older I-3. Subjects with transtibial amputations of either leg at least 1-year prior I-4. Suction or elevated vacuum suspension and Socket Comfort Score of at least 6 I-5. Sock fluctuation of ≤ 8 ply per day I-6. K-level rating of 3 or 4 based on the AMP Assessment Tool I-7. Ability to walk at a walking speed of > 0.75 meters per second with the current prosthesis I-8. Unilateral amputees (up to 7 bilateral amputees can be included, 1 per site in addition to the unilateral amputees who will be analyzed as a separate sub group) I-9. Foot size: 25-30 cm I-10. Ability to complete a continuous 6MWT I-11. Ability to provide written, informed consent |

| | |
|------------------------------------|--|
| | 
I-12. Ability to complete study visits and study documents
 
I-13. Ability to manage the complexity of a powered device including charging and changing batteries as needed
 
I-14. Ability to read and understand English
 |
| Key Exclusion Criteria | 
E-1. Subjects who have never used a prosthetic device
 
E-2. Less than 55 years of age
 
E-3. Weight <150 lbs. or > 287 lbs.
 
E-4. Transfemoral amputees
 
E-5. Active sores or ulceration on subject’s residual limb
 
E-6. Sore on contralateral foot
 
E-7. Cuff-link socket suspension
 
E-8. Socket Comfort Score less than 6
 
E-9. Sock fluctuation of > 8 per day
 
E-10. K level of 1 or 2
 
E-11. Amputation clearance < 8.625”
 
E-12. History of stroke or TIA that impairs current walking
 
E-13. Recent history of excessive falling defined as more than 2 falls requiring medical assistance in the prior year
 
E-14. Medications potentially affecting balance
 
E-15. Recent hospitalization (within past 3 months)
 
E-16. Cognitive deficiency that would impact ability to charge and change batteries as needed
 |
| Primary Statistical Methods | 
Subjects will be enrolled to characterize improvements with the emPOWER Ankle compared to the subject’s passive prosthesis. Data analysis will be descriptive in nature.
 |

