9.1. Screening

Subjects presenting to Investigators with transtibial amputations and who are currently using a passive prosthetic device will undergo evaluation for potential participation in the study.

A subject will sign the study-specific informed consent form (ICF) prior to performing any test involved in determining eligibility that goes beyond standard of care.

Each subject must meet the inclusion/exclusion criteria for this study to be eligible for study participation.

9.2. *Moment of Enrollment*

Subjects will be considered “enrolled” in the study once compliance with all inclusion and exclusion criteria has been verified and documented; and the subject has signed the informed consent form. At that point, the subject will enter the baseline phase of the study.

9.3. *Subject Identification*

Each subject will be assigned a unique subject identification number at the time of consent. This subject identification number will be retained throughout the study if the subject is enrolled. Sites will keep a log that notes the subject’s name and corresponding subject identification number. All case report forms (CRFs) will be tracked, evaluated, and stored using only the subject ID number and initials. No personal other identifying information will be included on the CRFs.

The ICF will notify subjects that study monitors, auditors, and representatives of government agencies will have access to personal identifying information to ensure that data reported on the CRFs corresponds to the person who signed the ICF and the information contained in the source documentation.

9.4. *Phase I: 1st Visit - Baseline*

For each of the enrolled subjects, characteristics at the time of the procedure including: age, sex, weight, amputation side(s) and amputation type(s), medical history will be recorded. At day of enrollment, subjects will complete:

- Amputee Mobility Predictor (AMP)
- Physical Assessment
- Fitted with a Fitbit® One™ activity tracker
 - The activity tracker will to be used to monitor steps taken on their passive prosthetic device for 14 days. A minimum of twenty-seven hundred (2700) recorded daily steps while using the passive prosthesis will be documented toward ability to perform the study’s 6MWT. [12]
- Subjects will be provided a patient diary to track activity, falls and self-reporting of activities of daily living.

9.5. *Phase I: 2nd Visit - Study Procedure*

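### Do five subjects in Section 9, up to ten elsewhere, and a cap of seven bilateral amputees at one site leave the sample undefined?

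*Combined protocol and SAP*

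**What the plan says.** **Number of subjects.** Section 9 (Study Visits) states that the study "aims to enroll five (5) subjects at one (1) study site". Section 7.3, just above it, says "The study will enroll up to ten (10) subjects into Phase I". The Synopsis gives the maximum twice. Its row on numbers and sites reads "Up to ten (10) subjects will be enrolled into this study at one (1) study site", and its Study Population row reads "The study population will include up to ten (10) unilateral transtibial amputees".

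**Bilateral amputees.** I-8 in Table 7.1.1 carries the allowance "up to 7 bilateral amputees can be included, 1 per site in addition to the unilateral amputees". The Synopsis version adds how they are to be handled: "1 per site in addition to the unilateral amputees who will be analyzed as a separate sub group". Section 7.3 asks the site for unilateral subjects. Section 9.2 counts a subject as enrolled "in the study once compliance with all inclusion and exclusion criteria has been verified and documented" and consent has been signed; it makes no distinction by amputation type.

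**Analysis.** The Synopsis says "Data analysis will be descriptive in nature". Section 11 defines the percent change in the six-minute walk test (6MWT) for a subject and says how to read its sign. It gives no sample size, analysis set or subgroup.

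**The concern.** Two enrolment figures that differ by a factor of two stand close together, with no sentence saying that one is a target and the other a limit. Neither has a rationale. The figure of seven bilateral amputees cannot be reached at one site, which suggests text carried over from a multi-site design. The references to each center in Section 16.3 and to authorship by site enrolment in Section 16.8 fit that impression.

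Three things could be at stake. A reader might not know how many subjects the primary 6MWT summary is meant to rest on. A bilateral subject might or might not use one of the ten places. And someone working from Section 11 alone might pool that subject with the unilateral amputees, where in so small a sample one person carries much of the mean.

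**Working it through.** **1. Can five or ten be reproduced?** No. The protocol gives no standard deviation, precision target, significance level or power, so neither figure can be derived. They can only be compared. Section 9 states an aim and the other places state a maximum:

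| Unilateral subjects enrolled | Against an aim of 5 | Against a maximum of 10 |
|---|---|---|
| 5 | met | within |
| 6 to 10 | exceeded | within |
| 11 | exceeded | breached |

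No enrolment from five to ten breaks either statement. The figure that binds is ten, and it is the same wherever a maximum is given. The ratio 10/5 = 2 compares a target with a limit.

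**2. What does the choice between five and ten affect?** Only precision. For illustration, take a two-sided 95% t-interval for a mean paired difference, which the protocol does not plan. Its half-width in standard deviations is t(0.975, n-1)/sqrt(n):

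- n = 5: 2.776/2.236 = 1.24
- n = 10: 2.262/3.162 = 0.72
- ratio: 1.2417/0.7154 = 1.74

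The difference is real, but it comes from how many subjects are recruited. Wording the target and maximum identically in three places would leave it as it is.

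**3. How many bilateral subjects can enter?** Sites x subjects per site = 1 x 1 = 1. Reaching seven would take 7/1 = 7 sites. The per-site limit is the tighter of the two and already binds, so changing seven to one would alter no enrolment decision.

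**4. Does the bilateral subject count toward the ten?** The Study Population row describes the ten as unilateral, and I-8 puts bilateral subjects on top of the unilateral ones. Together these give 10 + 1 = 11 at most. The looser wording in Section 7.3 and in the Synopsis row on numbers could be read as ten in all, that is 9 + 1. The two readings differ by one subject, and only if recruitment reaches the limit and a bilateral amputee is enrolled. At the Section 9 aim, 5 + 1 = 6 fits both. On either reading the unilateral summary rests on at most ten.

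**5. Would the bilateral subject be pooled?** The Synopsis version of I-8 calls for a separate subgroup. With at most one such subject, that can only mean reporting the person individually and leaving them out of the unilateral summary. Section 9.4 records amputation side and type at baseline, so the analyst can identify the subject. Section 11 is silent on the matter and does not contradict the Synopsis.

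If the rule were ignored, and an unweighted mean of percent changes were used (an assumption, since Section 11 names no summary statistic), an added subject would weigh 1/6 = 16.7% beside five or 1/11 = 9.1% beside ten. A difference of 10 percentage points from the unilateral mean, used only as a scaling unit, would move the pooled mean by 10/6 = 1.7 or 10/11 = 0.9 points. With the rule followed, the movement is zero.

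**The case for a change.** The strongest case for a change is that eligibility tables and statistical sections are what people work from. Table 7.1.1 omits the subgroup clause, and Section 11 names no analysis population, so the only safeguard sits in one Synopsis cell. The pooled weights above are also lower bounds. The primary comparison uses the 3-month 6MWT, and Section 9.7 places that visit in Phase II, to which subjects are invited, so fewer subjects may contribute than were enrolled. The correction would cost a few words and no data.

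Much of this stands as description. The clause is missing from both places, the seven is unreachable, and no text joins five to ten. The replacement rule in Section 7.2 does not join them either, since it covers only withdrawals before a subject walks on the device.

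What does not stand is the step from untidy wording to a wrong result. The Synopsis is part of the same protocol, and pooling requires setting it aside. Attendance at 3 months is a reason why harmonising the enrolment figures would not fix the primary denominator. One might also worry that a gap between aim and maximum lets the sponsor choose when to stop in an open-label study. A bare maximum of ten would allow the same latitude, so identical wording would not remove it.

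**Conclusion.** The inconsistencies are there, and they are clerical. Followed as written, the protocol enrols an aim of five and no more than ten unilateral subjects, admits at most one bilateral subject, and reports that person separately. The unresolved part is one subject in the overall maximum (ten or eleven), which arises only if every unilateral place is filled and a bilateral amputee is also enrolled. It does not touch the unilateral 6MWT summary.

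This rests on three readings: that an aim and a maximum are different kinds of figure, that the per-site limit in I-8 is applied as stated, and that the analyst takes the Synopsis subgroup rule as part of the plan. All are the ordinary readings. No hypothesis test, power statement or error rate depends on the number enrolled, so tidying the wording would change no analysis and no conclusion. It can be left for any amendment made for other reasons.

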9.7. Phase II: 4th Visit – 3 Month Visit

Subjects will be invited to participate in long-term follow-up. For a minimum of 14 days prior to this visit, the subject should wear the Fitbit and complete the patient diary for steps, fall and daily activity.

Subjects will be seen by the prosthetist after wearing the emPOWER Ankle for 3 months. The window for this visit is -1 week / + 6 weeks.

During this visit, the subject will complete the following study assessments wearing the emPOWER Ankle:

- 12MWT (with distance walked assessed at 6 and 12 minutes)
- 10MWT
- L-Test
- Ramp Ascent
- Ramp Descent
- ABC Scale
- Falls Efficacy Scale
- AMP
- Mobility PLUS-M (12 item Short Form)
- PROMIS Questionnaires
- Patient-specific Functional Scale (PSFS)
- Numeric Pain Rating Scale (NPRS)

In addition, the patient diary will be reviewed for Fitbit steps, falls and daily activity.

At the end of the study visit, subjects will return to wearing their passive prosthetic foot for 2-4 weeks of re-accommodation.

The subjects are reminded to wear the Fitbit activity monitor and complete the patient diaries to track activity, falls and self-reporting of activities of daily living.

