9.8. Phase II: 5th Visit – Crossover Visit

Subjects will be seen by the prosthetist after wearing their passive prosthetic foot for 2-4 weeks. The window for this visit is 2-6 weeks after passive device fitting.

For a minimum of 14 days prior to this visit, the subject should wear the Fitbit and complete the patient diary for steps, falls and daily activity.

During this visit, the subject will complete the following study assessments wearing the passive prosthetic:

- 12MWT (with distance walked assessed at 6 and 12 minutes)
- 10MWT
- L-Test
- Ramp Ascent
- Ramp Descent
- ABC Scale
- Falls Efficacy Scale
- AMP
- Mobility PLUS-M (12 item Short Form)
- PROMIS Questionnaires
- PSFS
- NPRS

At the end of the study visit, subjects will return to wearing the emPOWER Ankle for the remainder of the study. If there are any adjustments to the tuning settings different from those previously used for the emPOWER Ankle, the tuning record should be saved.

9.9. ***Phase II: 6th Visit – 6 Month Visit***

Subjects will be seen by the prosthetist. The window for this visit is -4 weeks / + 3 months.

During this visit, the subject will complete the following study assessments wearing the emPOWER Ankle:

- 12MWT (with distance walked assessed at 6 and 12 minutes)
- 10MWT
- L-Test
- Ramp Ascent
- Ramp Descent
- ABC Scale
- Falls Efficacy Scale
- AMP
- Mobility PLUS-M (12 item Short Form)
- PROMIS Questionnaires
- PSFS
- NPRS

If there are any adjustments to the tuning settings for the emPOWER Ankle, the tuning record should be saved.

9.10. ***Phase II: 7th Visit – 12 Month Visit (Final Study Visit)***

Subjects will be seen by the prosthetist. The window for this visit is -3 months / + 3 months. This will be the final study visit.

During this visit, the subject will complete the following study assessments wearing the emPOWER Ankle:

- 12MWT (with distance walked assessed at 6 and 12 minutes)
- 10MWT
- L-Test
- Ramp Ascent
- Ramp Descent
- ABC Scale
- Falls Efficacy Scale
- AMP
- Mobility PLUS-M (12 item Short Form)
- PROMIS Questionnaires
- PSFS
- NPRS

9.11. **Table 9.11.1: Procedures and Assessments**

The following table summarizes the timing and specific assessments to be conducted in this study:

| ASSESSMENT | BASELINE 1ST Visit | PASSIVE DEVICE ASSESSMENT/ ANKLE FITTING 2nd Visit | emPOWER Follow-Up 3rd Visit | 3 MONTHS 4th Visit | CROSSOVER 5th Visit | 6 MONTHS 6th Visit | 12 MONTHS 7^h Visit |

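### Section 9 and the 9.7/9.8 headings can be read as requiring benefit before the 3-month primary walk test; the Synopsis, 7.3 and the 9.7 text set no such condition

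*Combined protocol and SAP*

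**What the plan says.** **Text that places a condition before the primary visit.** Section 6.1 sets the primary endpoint as the 6MWT comparison at 3 months. Section 9 defines the phases: "Phase I will include all subjects enrolled in the study and followed through emPOWER Follow-up (Visit 3"). It then restricts who is offered the device and Phase II: "Subjects who show benefit from the emPOWER Ankle will be offered the opportunity to continue to use the emPOWER Ankle after the study and participate". No measure, threshold, visit or assessor for benefit appears anywhere. The 3-month visit in 9.7 carries a Phase II heading, and so does the passive re-test: "Phase II: 5th Visit – Crossover Visit".

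**Text without a benefit condition.**
- The Synopsis (Study Design) runs Phase I from screening to 3 months. Its Study Duration row gives the first phase about four months and makes the further 9 months the subject's choice.
- Section 7.3: "Subjects will then be invited to participate in Phase II, long-term follow-up".
- Section 9.7, opening line: "Subjects will be invited to participate in long-term follow-up".
- Section 6.2 and the Synopsis describe long-term follow-up, at 3, 6 and 12 months, of those willing to carry on with the device.
- Section 9.6 (Visit 3) lists no benefit decision, device return or exit procedure. Section 9.8 sends subjects back to the powered ankle without condition. Table 9.11.1 is one schedule for everyone.

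Section 14 has its own benefit-based offer of continued device use. It places the offer at the end of the study and keeps it from subjects until completion.

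**The concern.** A site cannot follow both sets of text. Section 15.5 demands exact adherence, and nothing says which section prevails. Visit 2 yields a passive 6MWT and Visit 3 a powered 6MWT, so a judgment of benefit at the end of Section 9's Phase I could rest on an early reading of the outcome itself. Subjects with small gains, whether truly small or small by chance, would then never reach the primary measurement.

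The rest of the plan would show this but not repair it. Section 16.1 reports data on every subject, so the loss would be visible. Section 7.2 provides for replacement only of subjects who leave before walking on the device. Section 11 gives a percent-change formula but no analysis set. Section 1.1 says the results are meant to support marketing and reimbursement, so a favourable tilt in the headline gain would matter even without a formal test.

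**Working it through.** The plan contains no calculation on this point to reproduce. Two checks apply.

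**1. Which phase boundary do the timings fit?**

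Inputs: Visit 1 to Visit 2, 14 days (9.4, step monitoring); fitting to Visit 3, 16 days, +1 week (9.5, 9.6); fitting to Visit 4, 3 months, taken as 91 days ("The window for this visit is -1 week / + 6 weeks"); Visit 4 to Visit 5, 2-4 weeks nominal, 2-6 weeks by window (9.8). One month is taken as 30.4 days.

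| Phase I ends at | Days | Months |
|---|---|---|
| Visit 3 (Section 9) | 14 + 16 = 30; with +1 week, 37 | 1.0-1.2 |
| Visit 4, nominal | 14 + 91 = 105 | 3.5 |
| Visit 5, nominal | 14 + 91 + 14 = 119 to 14 + 91 + 28 = 133 | 3.9-4.4 |
| Visit 5, full windows | 14 + 84 + 14 = 112 to 14 + 133 + 42 = 189 | 3.7-6.2 |

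The Synopsis gives the first phase about four months. Section 9's boundary does not fit. Crossover fits best, although ending at Visit 4 is not excluded. Both place the 3-month visit inside Phase I.

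For Phase II, the Synopsis figure of 9 months equals 12 - 3. Section 9's boundary would give 12 months less 16 days, about 11.5 months.

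Section 9 also "aims to enroll five (5) subjects at one (1) study site", whereas the Synopsis and 7.3 allow up to ten. That suggests, as an inference only, that Section 9 was not updated with the rest.

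**2. What would the gate do if applied?**

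Assume a subject's passive distance is b and the true device effect is d, with mean mu and SD sd. Each walk has independent error e with SD se, all normal. Then V2 = b + e2, V3 = b + d + e3, V4 = b + d + e4, V5 = b + e5. Take the gate as any gain at Visit 3: V3 - V2 = d + e3 - e2 > 0.

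- Gain against the Visit 2 passive walk: V4 - V2 = d + e4 - e2. Its covariance with the gate variable is sd² + se², which is positive.
- Gain against the Crossover passive walk: V4 - V5 = d + e4 - e5. Its covariance with the gate variable is sd², which is zero or positive.

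With s = sqrt(sd² + 2se²), a = -mu/s and lambda = pdf(a)/(1 - cdf(a)), the excess in the selected subjects is (sd² + se²)/s × lambda against Visit 2 and sd²/s × lambda against Crossover. The first is always toward the device. The second is toward the device, or zero if the true effect does not vary between subjects. The documents give no value for sd or se and no gate rule, so the formulas settle the sign and not the amount.

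**The case against.** **No gate operates at visit level.** Section 9 offers Phase II to those who benefit; it does not say that others are excluded. Visit 3 has no procedure for deciding benefit, and 7.3 and 9.7 invite without condition. A site working from the visit pages would take every willing subject to Visit 4. This stands, and it makes the gated reading the weaker one.

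**The Synopsis is not fully clear either.** Month 3 is both the end of its Phase I and the start of its Phase II. The Synopsis and 6.2 both list 3 months among the long-term visits. Nothing in it states that Phase I includes Crossover. This also stands: aligning Section 9 alone would not be enough, because the invitation would still leave the primary visit optional.

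**Stronger readings a reader might infer.**
- *The trial selects its primary population on response.* The documents do not support this; most of the text points the other way.
- *The bias can be sized.* It cannot. With assumed se of 15-30 m, sd of 0-30 m and a gate of any Visit 3 gain, the formulas above return 0 m (sd = 0, against Crossover) to about 28 m (mu = 0, sd = se = 30, against Visit 2: s = 52.0, lambda = 0.798, 1800/52.0 × 0.798 = 27.6 m). That spread reflects the assumptions, not this trial.
- *A benefit offer at Visit 3 contradicts Section 14.* That depends on what the study means. Section 9's words, "use the emPOWER Ankle after the study and participate in Phase II", can be read as treating Phase I as the study, while 9.10 calls month 12 the final study visit. The point is ambiguous.

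**Conclusion.** The inconsistency is real and certain on the text: both the phase boundary and the condition for passing it differ between Section 9 with the 9.7/9.8 headings and the Synopsis, 7.3 and the 9.7 text. The consequence is conditional. If all fitted subjects go on to Visits 4 and 5, the benefit-gate bias is zero. If a site applies Section 9 and judges benefit on something related to walking distance, the 3-month gain is biased toward the device. Only the direction can be claimed. In a single-site descriptive pilot of up to ten subjects, with no test and no success criterion, this is minor to should-fix.

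**What to change.** 1. Section 9: delete the benefit condition on Phase II and state that every subject fitted with the emPOWER is scheduled for Visits 4 and 5 whatever the Visit 3 result.
2. Relabel 9.7 and 9.8 as Phase I, and state in the Synopsis that Phase I runs through Crossover. This is inferred from the four-month duration; the Synopsis does not now say it.
3. Move the invitation to long-term follow-up from the start of 9.7 to the end of 9.8. In 6.2 and the Synopsis, limit voluntary continuation to the 6- and 12-month visits.
4. Keep the benefit-based device offer only in Section 14, at study end.
5. Section 11: take all fitted subjects as the primary set and report how many have no 3-month value.

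The cost is wording in the Synopsis, 6.2, 9, 9.7, 9.8 and 11. If a site would otherwise have applied the gate, a few more subjects may attend Visits 4 and 5, and the reported gain may be less favourable.
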